4 STUDY DESIGN

During this phase of the trial, 14 subjects will be assigned to one of two walking groups of 7 subjects each. The exercise intervention, PACE-Life, will last for 24 weeks and includes both group walks and independent walks (done at a location of the subject's choosing). Subjects will be asked to complete a total of 5 in-person assessments at screening, baseline, mid-point, post-test, and 1-month follow-up.

4.1 INTERVENTION

Groups will occur twice per week for 30 minutes for the entire intervention without changes in frequency and duration. The intensity, however, of both group walks and home-based walks will increase throughout this intervention in a stepwise fashion to create an exercise dose response to maximize impact on CRF. The rationale for this plan hinges on both the importance of maintaining cohesion and social interaction as well as the practicality concerns regarding sustainability. Furthermore, we tested a 2x/week group schedule in the pilot with high attendance rates and feedback (overall attendance: 84%). The intervention overviews are given below:

Weeks	# of Clinic-based Group Sessions	Duration of Group Sessions	# of Home-based Sessions	Duration of Home-based Sessions	Intensity
1-3	2	30 Minutes	0	30 Minutes	50-60% of HRR
4-6	2	30 Minutes	0	30 Minutes	50-65% of HRR
7-9	2	30 Minutes	1	30 Minutes	60-65% of HRR
10-12	2	30 Minutes	1	30 Minutes	65-70% of HRR
13-15	2	30 Minutes	2	30 Minutes	65-70% of HRR
16-18	2	30 Minutes	2	30 Minutes	65-70% of HRR
19-21	2	30 Minutes	3	30 Minutes	70% of HRR
22-24	2	30 Minutes	3	30 Minutes	70% of HRR

PACE-life will be integrated into the STEP outpatient clinics in Raleigh, NC and Carrboro, NC. The group walks will occur in the surrounding area around the clinics on sidewalks, bike trails, and residential streets. Goal setting groups and all assessments will take place in a conference room at the clinic.

4.1.1 GOAL-SETTING

Goal-setting will include setting goals for the upcoming week in terms of number of steps as well as how many intensity walks (at specified heart rate) that individuals plan to complete. Goal-setting materials draw upon SMART (specific, measurable, achievable, relevant, and time-based) principles as well as implementation intentions (i.e., if-then plans) and mental contrasting. Specifically, subjects will be asked to imagine what the best thing would be about walking/exercise more and then identify the biggest barriers. They will then be encouraged to create if-then plans about how to manage barriers to exercising more. This procedure has been extensively examined in social psychology research and has been shown to be successful in helping individuals increase their exercise (93). Goal-setting groups will be audiotaped and subsequently coded for fidelity to the protocol.

4.1.2 FITBITS

All subjects will be provided with a Fitbit that is labeled with a subject number. All Fitbits are paired to a Fitbit account with the username ([contact]) and password (pacelife). Data from Fitbit devices can be synced to the corresponding account and accessed through Fitbit.com. Subjects will be provided information about their accounts should they want to look at the data but will be asked not to change any of the settings as we will be using data for tracking steps/day and minutes spent walking. No identifying information will be inputted in the Fitbit.com account for subjects.

4.2 STUDY PROCEDURES AND MEASUREMENTS

4.2.1 SCREENING VISIT

The following measures will be examined at screening:

- Demographics- We will collect information on age, sex, ancestry, education, parent education, smoking, substance use, current medications, duration of outpatient treatment, and diet.
- Intelligence- In adherence with our inclusion criteria that subjects must have an IQ greater than 70, the Wechsler Abbreviated Scale of Intelligence (WASI) will be administered.
- Medical History- A licensed physician will complete the Medical History and Physical Exam Form. They will also complete a 10 minute physical to ensure health.
- Current Physical Activity- In order to ensure that subjects are healthy enough to begin the walking program, subjects will complete the Physical Activity Readiness Questionnaire (PAR-Q).
- Diagnosis-The Structured Clinical Interview for the DSM-V (SCID) will be utilized to assess symptoms. The SCID is a semi-structured interview that assesses for DSM diagnoses. The SCID will be used to verify that subjects have a schizophrenia spectrum diagnosis before they are enrolled in the study. Raters will be trained to conduct the SCID to a gold standard of reliability (i.e., intraclass correlation > .80).

4.2.2 BASELINE, MID-POINT, POST-TEST, 1 MONTH FOLLOW-UP

The following measures will be examined at the baseline, mid-point, post-test, and 1 month follow-up study visits:

- Demographics- We will collect information on age, sex, ancestry, education, parent education, smoking, substance use, current medications, duration of outpatient treatment, and diet.

- Minutes Spent Walking- We will utilize data recorded from Fitbits to assess minutes spent walking (by syncing Fitbits to corresponding Fitbit.com accounts and loading deidentified data onto study laptops).
- The Short Form International Physical Activity Questionnaire (IPAQ), a valid self-report measure, to assess changes in physical activity. The IPAQ Short Form is a four-item scale that assesses frequency and duration of walking, moderate-intensity exercise, vigorous-activity exercise, and sitting.
- Steps/day. We will also collect daily step numbers using Fitbit data downloaded onto study laptops from Fitbit.com at group sessions.
- Cardiorespiratory fitness (CRF)- CRF will be measured using the 6-minute walk test (6MWT) during which individuals are asked to walk continuously for six minutes on a flat, indoor surface around cones (separated by 100ft) and the primary outcome is the total distance walked. The 6MWT is recommended for use with sedentary individuals and to evaluate the impact of an exercise intervention. Moreover, the 6MWT has been successfully administered to individuals with SSDs, including those in our pilot trial. As a result, we plan to utilize the 6MWT as our primary measure of CRF.
- Self-determination Basic Needs. The self-determination basic needs of autonomy, relatedness, and competence will be measured with two scales. The Basic Psychological Need Scale-in General is a self-report measure that assesses general satisfaction with autonomy, relatedness, and competence. Three subscale scores are produced. The Basic Psychological Needs in Exercise Scale (BPNES) is self-report scale that measures the extent to which basic needs are satisfied through exercise.
- Symptoms- the Positive and Negative Syndrome Scale (PANSS) will be utilized to assess symptoms specifically present in schizophrenia spectrum disorders. The PANSS is a semi-structured interview assessing positive symptoms, negative symptoms, and general psychopathology symptoms. Raters will be trained to conduct the PANSS to a gold standard of reliability (i.e., intraclass correlation > .80)
- Resting Systolic/Diastolic Blood Pressure and RHR will be assessed following standardized procedures at the STEP clinic. Individuals with SSDs will be placed in a sitting position in a quiet room, with lights dimmed, and will be asked to remain quiet and relaxed with their eyes closed while avoiding movement for approximately 10 minutes. After 10 minutes, research team members will assess their RHR via palpation for 1 minute. Following the assessment of RHR, resting BP will be assessed using an automated blood pressure device following the manufacture standard procedures. Given the high rates of hypertension in this population, the assessments of blood pressure changes throughout this exercise intervention are significant indicators of potential benefits of exercise on improvements in physical health. Further, given the sedentary lifestyle of many individuals with SSD, changes in RHR upon the initiation of exercise is a valuable indicator of fitness and physical health.
- Autonomous Motivation- Given the available research indicating that autonomous motivation is related to negative symptoms and subsequent engagement, maintenance, and adoption of exercise in individuals with SSDs, we will measure this construct with The Behavioral Regulation in Exercise Questionnaire-2 (BREQ-2).

- **Enjoyment of Walking-** Given that enjoyment of the walking program can impact adherence to the treatment, we will measure this construct with the Physical Activity Enjoyment Scale (PACES).
- **Planned Behavior-** Available research has shown that intentions, self-efficacy, attitudes and norms are correlated to adherence in exercise. All items are derived from established measures of theory of planned behavior variables (e.g., Conner & Sparks, 2015). Responses are all on 7-point scales. The order of items would be randomized.
- **Loneliness:** The UCLA Loneliness Scale is a brief self-report measure that will be used to assess this construct.
- **Weight, BMI, and Waist/hip Circumference-** We will measure weight, BMI, and waist/hip circumference at all assessments using the scale and measuring tape located at the STEP clinic.
- **Exit Survey on PACE-life-** At the conclusion of the open trial, we will administer a brief questionnaire to the subjects regarding satisfaction and acceptability that will have both forced choice and open-ended questions.

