Sports Medicine guidelines. (If an individual answers yes to one item on the of the Physical Activity Readiness Questionnaire (PAR-Q), she/he will be asked to get clearance from a physician prior to participating in the study)

8. Willing and able to provide informed consent.

Exclusion Criteria

1. Pregnant women will be excluded because pregnancy alters autonomic and immune responsiveness, increase weight gain, and can influence heart rate.

Number Of Subjects	14 individuals with schizophrenia spectrum disorders
Study Duration	Each subject’s participation will last 7 months, 6 months of intervention and a 1 month follow-up
Study Phases	Pre- Screening- Will be completed prior to the first in-person visit via a telephone screen for study eligibility.
Screening	
Study Treatment	Screening- Subjects who are deemed eligible will be brought on site to obtain consent and complete the screening assessments (Demographics, WASI, a licensed physician will complete a medical history and physical exam, PAR-Q.
Follow-Up	Baseline, Mid-point, Post-test, and 1-Month Follow-up- Subjects will complete the Demographics, Minutes Spent Walking, the Positive and Negative Syndrome Scale (PANSS), the Short Form International Physical Activity Questionnaire (IPAQ), Steps/day, Cardiorespiratory fitness (CRF)- CRF will be measured using the 6-minute walk test (6MWT), Self-determination Basic Needs, the Basic Psychological Need Scale-in General, the Basic Psychological Needs in Exercise Scale (BPNES), Resting Systolic/Diastolic Blood Pressure and resting heart rate (RHR), autonomous motivation will be measured with the Behavioral Regulation in Exercise Questionnaire-2 (BREQ-2), enjoyment of walking will be measured with the Physical Activity Enjoyment Scale (PACES), the UCLA Loneliness Scale, Weight, BMI, and Waist/hip Circumference: study intervention/experimental treatment. At the baseline assessment, subjects will be provided with a Fitbit wristband and instructed how to use it. At the conclusion of the trial, investigators will administer a brief questionnaire to the subjects regarding satisfaction and acceptability.
	Study Treatment- Walking groups will occur twice per week for 30 minutes. The intensity of both group walks and home-based walks will increase throughout this intervention in a stepwise fashion to create an exercise dose response to maximize impact on CRF.

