3 ASSESSMENT OF DATA

At this stage of treatment development, specific outcomes include:

1. Feasibility (Can PACE-life be delivered within this treatment setting?)
 - Will determine if recruitment procedures yield the target number of subjects in 3 months
 - Will determine feasibility of assessments based on subject compliance rates
2. Tolerability (How well is PACE-life accepted by the subjects?)
 - Will be evaluated by examining subject attendance to groups, adherence to homebased component of program, Fitbit usage, and dropout rates.
3. Intervention adherence
4. Evaluation of PACE-life. We will evaluate feasibility in two ways. First, we will determine if recruitment procedures yield the target number of subjects in 3 months. Second, we will determine feasibility of assessments based on subject compliance rates. The tolerability of PACE-life will be evaluated by examining subject attendance to groups, adherence to homebased component of program, Fitbit usage, and dropout rates.

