5 STATISTICAL ANALYSES

5.1 DATA ANALYTIC PLAN

Feasibility will be defined by our ability to meet our recruitment targets (14 people), frequency of engagement in the intervention by participants (group attendance and activity tracking/home-based adherence), and feedback on the intervention from participants. Feedback from participants will be incorporated into modifying the manual for the RCT.

Analyses of intermediate and primary outcomes will primarily be descriptive in nature. We will calculate means, standard deviations, and within-group effect sizes of intermediate targets (SDT needs and autonomous motivation), proximal outcomes, including minutes spent walking, and steps/day, the primary outcome of CRF, and the secondary outcomes including RHR, blood pressure, loneliness, and symptoms. Further, we will calculate the percentage of the sample meeting the threshold for clinically significant changes in our outcomes of 6MWT, steps/day, and minutes spent walking to determine whether these changes are clinically meaningful. Finally, we will explore the relationship between baseline IQ, treatment adherence and outcome improvement so as to determine if cognitive functioning is associated with treatment response.

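### The exit survey has a single end-of-trial occasion and no procedure for subjects who withdraw, so the feedback used for feasibility and the RCT manual may over-represent completers

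*Protocol*

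**What the plan says.** Protocol section 4.2.2, under the exit survey, states: "At the conclusion of the open trial, we will administer a brief questionnaire to the subjects regarding satisfaction and acceptability". The form has closed and open questions. The synopsis (Study Phases) gives the same timing: "At the conclusion of the trial, investigators will administer a brief questionnaire to the subjects regarding satisfaction and acceptability".

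Section 5.1 defines feasibility by three things: reaching the recruitment target of 14, engagement with the intervention, "and feedback on the intervention from participants". It then gives that feedback a further use: "Feedback from participants will be incorporated into modifying the manual for the RCT".

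Section 3 poses the tolerability question, "How well is PACE-life accepted by the subjects", and says how it is answered: "Will be evaluated by examining subject attendance to groups, adherence to homebased component of program, Fitbit usage, and dropout rates". The exit survey is not in that list.

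Section 4 lists five in-person assessments: screening, baseline, mid-point, post-test and 1-month follow-up. None is tied to early withdrawal. The only follow-up described after withdrawal is safety follow-up in section 7.2. The SAP mentions neither the exit survey nor dropouts.

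**The concern.** A satisfaction survey held only at the end is answered most readily by those still present. If staying is related to liking the programme, the respondents are partly selected on what the survey measures. The Protocol makes that link plausible: section 4.2.2 justifies the enjoyment scale (PACES) on the ground that enjoyment can affect adherence.

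Two products of the trial depend on this feedback: one of the three parts of the feasibility definition, and the revision of the manual. Developing the manual and examining feasibility are both stated aims (section 3.1). People who leave can say what made the programme hard to continue, and section 1 presents the stepwise design partly as a way to reduce dropout. Without recorded reasons, the trial could report how many left but not why.

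**Working it through.** The plan states no figure on this point, and section 5.2 declines a power analysis, so there is nothing to reproduce. The check compares the relevant sections and then bounds the possible effect.

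**1. What each kind of subject contributes.** This assumes that a person who leaves also stops attending assessments. Mid-point is 3 months (section 3.1). PACES, BREQ-2, the exercise-needs scale and the planned-behaviour items are listed for baseline, mid-point, post-test and 1-month follow-up (section 4.2.2).

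| Subject | Exit survey | On-treatment self-report | Attendance, adherence, Fitbit data | Reason for stopping |
|---|---|---|---|---|
| Leaves before mid-point | no stated occasion | none | yes, until stopping | not planned |
| Leaves after mid-point | no stated occasion | mid-point | yes, until stopping | not planned |
| Completes | yes | mid-point and later | yes | not applicable |

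The first row is the clear gap. In the section 4.1 table, home sessions begin in week 7 and the intensity band changes at weeks 7-9 and again at weeks 10-12. Someone who stops at those steps has left before the first on-treatment PACES. PACES is also missing from the outcomes named in section 5.1 and from the SAP, so no analysis of it is specified.

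**2. Delay if leavers are contacted at the end.** The intervention lasts 24 weeks, and the SAP puts the last visit at up to 28 weeks. A subject who stops in week 8 would be asked 24 − 8 = 16 weeks later, or up to 28 − 8 = 20 weeks later. No contact route is stated.

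**3. Bounds on satisfaction among all enrolled.** Let n = 14, and let d be the number who do not answer. If all n − d respondents are satisfied, the survey shows 100%, while the share among all enrolled lies between (n − d)/n and 100%.

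| d | Respondents | Lower bound |
|---|---|---|
| 1 | 13 | 13/14 = 92.9% |
| 2 | 12 | 12/14 = 85.7% |
| 3 | 11 | 11/14 = 78.6% |
| 4 | 10 | 10/14 = 71.4% |
| 5 | 9 | 9/14 = 64.3% |
| 6 | 8 | 8/14 = 57.1% |

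The documents give no expected dropout for this trial. The only related figure is 76% completion in a stepwise programme for breast cancer survivors (section 1). Used purely as an illustration, 14 × 0.76 = 10.6, so about 11 complete and 3 do not.

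**4. Chance that the issue arises.** With an assumed dropout rate p and independent subjects, P(at least one dropout) = 1 − (1 − p)^14. This is 77% at p = 0.10, 96% at p = 0.20 and 98% at p = 0.24.

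**5. What drives the size.** If a share a of respondents and a share b of non-respondents are satisfied, the respondents' figure differs from the all-enrolled figure by (d/n) × (a − b). With d = 3, d/n = 21.4%, so the difference is 21.4% of the gap a − b. It is zero if a = b, at most 21.4 percentage points if a = 100% and b = 0%, and negative if leavers were the more satisfied. The documents give neither a nor b.

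**The case against.** Several points on the other side stand.

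- A reader might infer that dropouts are not asked. The text does not say so: the survey goes to the subjects, not to completers, and someone who stopped walking could still be contacted at the end. What can be said is that no procedure for reaching them is given.
- A reader might infer that tolerability is judged only by those who stayed. It is not. Section 3 uses attendance, home adherence, Fitbit use and dropout, so leavers count. Those who leave after mid-point have also given PACES and other self-reports, and adverse events are documented for everyone (section 7.1). Nor does section 5.1 restrict feedback to the exit survey.
- A reader might infer that leaving means disliking the programme. The documents do not establish this. Section 1 reports that waning attendance in an earlier trial was attributed to hospitalizations and social issues. The Protocol adds that falling motivation may also have contributed, and recorded reasons are what would separate these explanations.
- A reader might put a definite figure on the upward bias. Any such figure needs assumed satisfaction levels for completers and dropouts, and the result follows directly from the gap chosen. The plan also defines no acceptability percentage, threshold or go/no-go rule that a bias could tip.

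These points limit the claim but do not remove it. Attendance and dropout show that people left, not why. The exit survey is the only instrument described as asking about satisfaction and acceptability, and its one stated time would miss early leavers or reach them months late.

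**Conclusion.** The concern holds in a limited form. The Protocol has one end-of-trial occasion for the exit survey, no procedure for surveying subjects who withdraw, and no recording of reasons for stopping. Feedback that feeds the feasibility definition and the RCT manual may therefore over-represent completers, most clearly relative to those who leave before 3 months.

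The size cannot be determined from the documents. The illustration of 78.6% to 100% rests on two assumptions: 3 of 14 do not answer, and all 11 respondents are satisfied. An upward direction is plausible but not established. The 6-minute walk primary outcome and the section 3 tolerability measures do not depend on this survey. The change is worth making because it is cheap and bears on stated aims.

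**What to change.** In the synopsis (Study Phases) and section 4.2.2, keep the survey at the conclusion of the trial for subjects still taking part, and add a sentence along these lines:

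> The same form, with one added question on the reason for stopping, will be offered in person or by telephone when a subject withdraws or is recorded as a dropout.

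The Protocol counts dropouts without defining one, so the same edit should state what triggers the offer.

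In section 5.1, add that the number of exit-survey respondents will be reported out of all enrolled, with responses shown separately for completers and non-completers. If data collection has already ended, this reporting step can still be applied.

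The cost is a few short calls using the existing form. Some who leave will decline, so the data will remain incomplete, and the satisfaction results may be less favourable than those from completers alone.

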5 STATISTICAL ANALYSES

5.1 DATA ANALYTIC PLAN

Feasibility will be defined by our ability to meet our recruitment targets (14 people), frequency of engagement in the intervention by participants (group attendance and activity tracking/home-based adherence), and feedback on the intervention from participants. Feedback from participants will be incorporated into modifying the manual for the RCT.

Analyses of intermediate and primary outcomes will primarily be descriptive in nature. We will calculate means, standard deviations, and within-group effect sizes of intermediate targets (SDT needs and autonomous motivation), proximal outcomes, including minutes spent walking, and steps/day, the primary outcome of CRF, and the secondary outcomes including RHR, blood pressure, loneliness, and symptoms. Further, we will calculate the percentage of the sample meeting the threshold for clinically significant changes in our outcomes of 6MWT, steps/day, and minutes spent walking to determine whether these changes are clinically meaningful. Finally, we will explore the relationship between baseline IQ, treatment adherence and outcome improvement so as to determine if cognitive functioning is associated with treatment response.

